1 PROTOCOL SUMMARY

1.1 SYNOPSIS

Title: **The Development and Pilot Testing of a Caregiver-Child Shared Decision-Making Intervention to Improve Asthma in Urban Youth**

Grant Number: **1R21NR019668**

Study Description: This is a feasibility trial of a brief shared decision-making intervention that primary care providers will deliver to caregivers and their children aged 10-14 during a routine office visit, focusing on improving self-management. Brief shared decision-making will be compared to a dose-matched attention control; providers will be randomized to deliver either the active (n = 43) or control (n = 42) intervention to dyads (N = 85) who will be followed for 3-months. The trial will be informed by focus groups (caregivers separately (n = 20) ; early adolescents separately n = 20) and dyads (n = 20) (N=60).

Objectives:

1. **To develop BREATHE-PEDS in a pediatric population (dyads of caregivers and their 10- to 14-year-old early adolescents with uncontrolled asthma) receiving asthma care in FQHCs;**
2. **To evaluate the feasibility and acceptability of intervention procedures; and**
3. **To assess intervention effects on asthma outcomes (monthly x 3 months post-intervention).**

To accomplish these aims the proposed study includes two phases: (1) a development phase where we will develop **BREATHE-PEDS** using focus groups. Participants (N = 60) will include early adolescents (n = 20), caregivers (n = 20) and dyads (n=10 dyads) to adapt **BREATHE-PEDS**, and (2) a pilot validation phase where we will conduct a group-randomized trial in two FQHCs with 85 dyads treated by 8 PCPs (10 dyads/PCP) randomized to 1 of 2 study arms: (a) **BREATHE-PEDS** (n=42 dyads), or (b) dose-matched attention control (n=43 dyads). We will conduct post-trial interviews with PCPs, caregivers, and their children to evaluate satisfaction with the intervention; we will follow caregiver-child dyads for 3 months post-intervention to assess the impact of **BREATHE-PEDS** on asthma outcomes.

Hypotheses:

1. The intervention will be feasible and acceptable as evidenced by: high rates of dyad recruitment and retention; PCP fidelity to the intervention protocol; and PCP and caregiver-child dyad satisfaction.
2. Over 3-months post-intervention, relative to controls, **BREATHE-PEDS** children will have improvement (a) in asthma control as measured by the *Asthma Control Questionnaire*⁶³⁻⁶⁵ (primary outcome), higher perceived SDM, and (b) on other asthma outcomes (secondary outcomes), including quality of life, school absences, lung functioning, and exacerbation.

Endpoints:

NAME: Asthma Control Questionnaire
TYPE: Primary
TIME FRAME: Focus groups, Baseline and 1-, 2-, and 3-months post intervention

DESCRIPTION: 6-item validated and widely used measure of asthma control
WHO COMPLETES: Child with help from caregiver as needed

NAME: Shared Decision-Making Questionnaire— 9 items
TYPE: Secondary
TIME FRAME: Focus groups, Immediately after the medical visit (i.e., immediate post-intervention)
DESCRIPTION: 9-item validated measure of the decisional process in medical visits from both patients' and physicians' perspectives
WHO COMPLETES: Child AND Caregiver (PATIENT version) and PCP (clinician version)

NAME: Medication Adherence Record Scale-Asthma
TYPE: Secondary
TIME FRAME: Focus groups, Baseline and 1-, 2-, and 3-months post intervention
DESCRIPTION: 10-item validated measure of inhaled corticosteroid adherence (ICS) (dichotomized as high or not). Scores have been shown to predict Self-management as measured by objective electronic monitoring and prescription refill rates.
WHO COMPLETES: Child with help from caregiver as needed

NAME: Conventional and Alternative Management for Asthma
TYPE: Secondary
TIME FRAME: Focus groups, Baseline and 3-months post intervention
DESCRIPTION: 17-item validated measure of erroneous asthma management beliefs (9 items) and ICS beliefs (8 items)
WHO COMPLETES: Child with help from caregiver as needed AND Caregiver

NAME: Pediatric Asthma Quality of Life Questionnaire
TYPE: Secondary
TIME FRAME: Focus groups, Baseline and 1- and 3-months post intervention
DESCRIPTION: 23 questions in 3 domains (symptoms, activity limitation and emotional function). The activity domain contains 3 'patient-specific' questions. Children are asked to think about how they have been during the previous week and to respond to each of the questions on a 7-point scale (7 = not bothered at all - 1 = extremely bothered). The overall PAQLQ score is the mean of all 23 responses and the individual domain scores are the means of the items in those domains
WHO COMPLETES: Child with help from caregiver as needed

NAME: Pediatric Asthma Caregiver's Quality of Life Questionnaire
TYPE: Secondary
TIME FRAME: Focus groups, Baseline and 1- and 3-months post intervention
DESCRIPTION: 13-item in two domains (activity limitation and emotional function). Parents recall the impact that their child's asthma has had during the previous week and score each question on a 7-point scale.
WHO COMPLETES: caregiver

NAME: Asthma Impairment and Risk Questionnaire (AIRQ) BASELINE
TYPE: Secondary
TIME FRAME: Focus groups, Baseline and 1-, 2-, and 3-months post intervention
DESCRIPTION: 10-item valid and reliable survey that measures both domains of control: symptom impairments and risk for uncontrolled asthma
WHO COMPLETES: Children aged 12 and older

NAME: Asthma Impairment and Risk Questionnaire (AIRQ) FOLLOWUP
TYPE: Secondary
TIME FRAME: 1-, 2-, and 3-months post intervention
DESCRIPTION: 10-item valid and reliable survey that measures both domains of control: symptom impairments and risk for uncontrolled asthma
WHO COMPLETES: Children aged 12 and older

NAME: Brief debriefing survey
TYPE: Secondary
TIME FRAME: Immediately after the medical visit
DESCRIPTION: 10-item (caregiver) and 5-item (PCP) yes/no/short answer survey that asks the participant to recount what happened at the visit
WHO COMPLETES: Three versions Caregiver, Patient AND PCP

NAME: Asthma exacerbation
TYPE: Secondary
TIME FRAME: 1-, 2-, and 3-months post intervention
DESCRIPTION: Oral steroid use 1 year pre- through 1-year post-intervention; report of asthma-related acute care visits, ED visits, and hospitalizations; or Intensification of bronchodilators (to be defined by SMC). All self-reported and/or extracted from provider notes in the electronic health record, confirmed by claims data where available.
WHO COMPLETES: Child and Caregiver

NAME: Asthma Responsibility Questionnaire

Miscellaneous:

TYPE: Secondary
TIME FRAME: Focus groups, Baseline and 1- and 3-months post intervention
DESCRIPTION: 10-item validated measure assessing who is responsible for various asthma care tasks
WHO COMPLETES: Child and Caregiver

NAME: Newest Vital Sign
TYPE: Other
TIME FRAME: Focus groups, Baseline
DESCRIPTION: 6-item validated and widely used measures of health literacy
WHO COMPLETES: Caregiver

NAME: Short Assessment of Health Literacy-Spanish and English
TYPE: Other
TIME FRAME: Focus groups, Baseline
DESCRIPTION: Validated measures of health literacy
WHO COMPLETES: Caregiver

NAME: Asthma Prevention Index
TYPE: Other
TIME FRAME: Baseline and 1-, 2-, and 3-months post intervention
DESCRIPTION: 11 item index measuring how many steps and the regularity in which the steps are taken to prevent symptoms from occurring.
WHO COMPLETES: Child and Caregiver

Asthma history (e.g. age at diagnosis); Demographics
TYPE: Other
TIME FRAME Baseline
WHO COMPLETES: Caregiver

Study Population:

Aim 1: Focus groups (pre-trial). We will enroll caregivers (n =20) ; early adolescents (n =20) and dyads (n =10) (N=60) into separate focus groups.

Aims 2 & 3: Group-randomized trial. We will recruit 85 dyads and 8 clinicians to the trial.

Aims 2 & 3: Post-trial interviews. We will do post-trial interviews with a purposive sample of ~6 participating clinicians, ~10 early adolescents, and ~10 caregivers.

Inclusion of Women.

Caregiving participants in focus groups and the group-randomized trial. We anticipate enrolling more female caregivers than men because more women serve in the caregiving role. We therefore estimate that ~75% of our caregiving participants in this trial will be female. We will explore if there is a differential intervention effect by sex.

Provider participants (group-randomized trial). Based on the sex of the clinicians working at these sites, we anticipate that 75% of our 16 clinicians will be female.

Inclusion of Minorities.

Patient participants in focus groups and the group-randomized trial. Asthma prevalence and morbidity is increased in Latino (defined as a person of Cuban, Mexican, Puerto Rican, Cuban, South or Central American, or other Spanish culture or origin, regardless of race) and Black (defined as a person having origins in any of the black racial groups of Africa) youth. They also have more asthma-related emergency department (ED) visits and hospitalizations. To address these health disparities, we have partnered with Urban Health Plan, Inc. (UHP), a federally qualified health center (FQHC) that serves a predominantly Latino and/or Black community. Based on demographic data provided by UHP we anticipate that 95% of the adolescents will be ethnic-racial minorities with 85% Latino and 10% non-Hispanic Black; the racial/ethnic distribution of their caregivers is expected to be similar. Our team has extensive experience working in ethnically diverse populations, particularly in the context of asthma intervention research.

Provider participants (group-randomized trial). The racial and ethnic distribution of the PCP sample is expected to be approximately 50% Black, 45% White, 5% Asian, and 10% Hispanic; this is based on our prior experience with research involving FQHCs.

Post-trial interviews with clinicians, patients and caregivers. We will purposively sample to ensure a racial and ethnic diversity among our participants.

Other Vulnerable Populations.

Pregnant women will be eligible to participate since improving asthma control for their early adolescent children would benefit the family.

Description of Sites/Facilities Enrolling Participants:	Participants will be recruited from 3 Urban Health Plan sites. They include: El Nuevo San Juan [name] Adolescent Health and Wellness [name] Bella Vista [name]
Description of Study Intervention/Experimental Manipulation:	BREATHE-PEDS utilizes Primary Care Providers (PCPs) to deliver a brief tailored , shared decision-making intervention using motivational interviewing in a one-time 9-minute intervention during medical visits for asthma. PCPs will follow a 4-step script that was created by and tailored to black adults' asthma and inhaled corticosteroid beliefs, as well as their Asthma Control Questionnaire (ACQ) score, measured just prior to the medical visit. Step 1: Raise the subject (1½ minute). Step 2: Provide feedback (1½ minutes). Step 3: Enhance engagement (3 minutes). Step 4: Shared decision-making (3 minutes). Dose-matched Attention Control Condition. Control participants will receive a PCP-led 9-minute scripted discussion of healthy lifestyles (e.g., diet) following principles of Teach to Goal. Review of BMI, current diet and exercise: (3 minutes). Diet/exercise counseling: (3 minutes). Plan for goal attainment (3 minutes).
Study Duration:	Three months post intervention.
Participant Duration:	Pre-trial focus groups. One 2-hour session Group-randomized trial: Patient participants – 3 months Clinician participants = ~ 6 months (delivering the intervention one time to 12-13 patients during a single office visit) Post-trial interviews. One hour.

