9 STATISTICAL CONSIDERATIONS

9.1 STATISTICAL HYPOTHESES

Specific Aims:

1. To develop **BREATHE-Peds** in a pediatric population (dyads of caregivers and their 10- to 14-year-old early adolescents with uncontrolled asthma) receiving asthma care in FQHCs;
2. To evaluate the feasibility and acceptability of intervention procedures; and
3. To assess intervention effects on asthma outcomes (monthly x 3 months post-intervention).

Hypotheses:

1. The intervention will be feasible and acceptable as evidenced by: high rates of dyad recruitment and retention; PCP fidelity to the intervention protocol; and PCP and caregiver-child dyad satisfaction.
2. Over 3-months post-intervention, relative to controls, **BREATHE-Peds** children will have improvement (a) in asthma control as measured by the Asthma Control Questionnaire (primary outcome), higher perceived SDM, and (b) on other asthma outcomes (secondary outcomes), including quality of life, school absences, lung functioning, and exacerbation.

MEASURES / ENDPOINTS.

Primary Outcomes: asthma control as measured by improvements in Asthma Control Questionnaire (ACQ) score.

Secondary outcomes: (a) shared-decision-making as measured by scores the Shared Decision-making Questionnaire – 9 items, (b) Self-management as measured by the Medication Adherence Report Scale – Asthma (MARS-A), (c) asthma and ICS beliefs as measured by the Conventional and Alternative Management for Asthma, (d) asthma quality of life as measured by the Pediatric Asthma Quality of Life Questionnaire (PAQLQ) and Pediatric Asthma Caregiver's Quality of Life Questionnaire; and significantly lower rates of (e) asthma exacerbations, (f) symptoms days, (g) nights woken, (h) activity limitations, (i) shortness of breath, (j) wheeze, and (k) rescue medicine use. We will also track Asthma Impairment and Risk questionnaire and Asthma Responsibility Questionnaire scores over time.

Other measures: (1) demographics (age, sex); (2) health literacy as measured by the Newest Vital Sign and the Short Assessment of Health Literacy-English and Spanish; (3) asthma history and (4) lung function as measured by spirometry (COVID permitting).

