9.2 SAMPLE SIZE DETERMINATION

Power & Sample Size. With a sample size of 10 patients/PCP and 4 PCPs in each intervention arm (total $n=10*4*2=80$), and 20% attrition, we calculated the power to test the effect of intervention on outcomes. Power calculations were based on: (1) 4 repeated observations over the 3-month follow-up with a correlation of $p=0.8$ between repeated measures; (2) intra-cluster correlation among PCPs=0.2 to account for clustering of patients from the same PCP; and (3) LMMs to estimate pre- and post-intervention differences. We estimated an 80% power to detect a small effect size ($d=0.15$). For ACQ, this is equivalent to detect a post-intervention difference of 0.15 (assuming $SD=0.9$).

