9.4.2 ANALYSIS OF THE PRIMARY AND SECONDARY ENDPOINT(S)

Analytic Plan.

Aims 1 & 2: Development and Intervention Feasibility. We will document our success in meeting recruitment and randomization goals, as well as process (recruitment outreach and numbers meeting eligibility criteria who accept or decline enrollment) and implementation assessments (retention rates, data completion rates, as well as fidelity, contamination and masking in the clinical trial arm).

Randomization. This is a group-randomized trial in which the primary care providers (PCPs) will be randomized within sites to the active and control conditions. We will utilize a stratified block randomization plan, stratifying by provider type (physician vs. nurse practitioner/physician assistant), to insure equal numbers of PCPs within each PCP type are assigned to each condition. Randomization lists will be computer-generated in advance by our biostatistician. Outcomes will be analyzed at the level of the early adolescent and/or caregiver.

Masking. Participants and data collectors will be masked to study hypotheses and group assignment; the investigators will be blinded to group assignment. PCPs in both intervention conditions will use tablets as part of their respective interventions and have sessions audio-recorded, facilitating masking of participants and data collectors.

Aim 3: Intervention Effects. Intervention effects will be assessed using linear mixed models (LMM) or generalized linear mixed models (GLMM) for continuous and categorical outcomes, respectively. All hypothesis tests will be two-sided at level $\alpha=0.05$. The key outcome will be ACQ score; secondary measures will be examined to inform the future RCT. Separate models will be fitted for different outcome measures. If y_{ijt} is the outcome for patient j of provider i at time t , without loss generality then the following LMM will be used:

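### The MARS-A adherence score is cut to high or not high with no cut-point or reason, which costs precision; how much depends on assumptions the plan does not give

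*Combined protocol and SAP*

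**What the plan says.** The endpoint list in Section 1.1 calls MARS-A a "10-item validated measure of inhaled corticosteroid adherence (ICS) (dichotomized as high or not". It is collected at baseline and at 1, 2 and 3 months. The same entry supports the instrument by saying that its scores predict electronically monitored self-management and refill rates. It offers no such support for the two-level version.

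Section 9.1 lists the secondary outcome as "b) Self-management as measured by the Medication Adherence Report Scale – Asthma (MARS-A" and does not mention a split; Section 3 does the same. Section 9.4.2 assigns models by outcome type, "linear mixed models (LMM) or generalized linear mixed models (GLMM) for continuous and categorical outcomes" respectively, but does not say which applies to MARS-A. It adds that "secondary measures will be examined to inform the future RCT".

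No section gives a cut-point, an expected proportion high, a score distribution, or a power figure specific to MARS-A.

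**The concern.** Self-management is the behaviour the intervention is built to change. A high/not-high variable records a change only when a child crosses the threshold. Section 6.1.1, Step 4, gives an example in which the agreed short-term plan is a partial level of adherence. Whatever the clinical merits of that example, on which I take no view, it shows that the script counts a partial gain as progress. A two-level outcome may score that child as unchanged.

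Three things are at stake:

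- **Precision.** The between-arm estimate for MARS-A is less precise than the collected data allow.
- **Usefulness for the next trial.** A mean difference, an SD and a provider-level correlation on the score inform a future design better than a two-level split observed across eight providers.
- **Prespecification.** Section 9.4.1 puts a review of the data distribution before testing. With no cut-point written down, the plan leaves open that the threshold is set after the data are seen.

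**Working it through.** The plan states no MARS-A figure to reproduce. The 80% power for d = 0.15 in Section 9.2 is a separate question and is not used here. The check asks how much information a split loses under stated assumptions.

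**Inputs from the documents (Section 9.2)**
- "With a sample size of 10 patients/PCP and 4 PCPs in each intervention arm": 10 × 4 × 2 = 80 dyads.
- 20% attrition: 80 × 0.8 = 64 retained, or 64/8 = 8 per provider.
- ICC by provider 0.2; correlation between repeated measures 0.8.

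**Assumptions not in the documents**
- The MARS-A score is roughly normal.
- The proportion p in one category lies between 50/50 and 80/20.
- The ICC of 0.2 and the correlation of 0.8 apply to MARS-A.
- The treatment effect is a modest shift in the score.

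**1. One comparison, independent children.** Efficiency of the split relative to the score is E = φ(z_p)² / [p(1−p)].
- 50/50: 0.3989² / 0.25 = 0.637, loss 36%.
- 70/30: 0.3477² / 0.21 = 0.576, loss 42%.
- 80/20: 0.2800² / 0.16 = 0.490, loss 51%.
- 90/10, outside the assumed range: 0.1755² / 0.09 = 0.342, loss 66%.

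**2. One post-intervention comparison, clustered by provider.** Splitting a normal score also shrinks its ICC. From the bivariate normal, a score ICC of 0.2 becomes 0.128, 0.119 and 0.105 at the three splits. The efficiency is E × [1 + 7(0.2)] / [1 + 7(binary ICC)]; the numerator is 2.4.
- 50/50: 0.637 × 2.4 / 1.897 = 0.81, loss 19%.
- 70/30: 0.576 × 2.4 / 1.832 = 0.75, loss 25%.
- 80/20: 0.490 × 2.4 / 1.736 = 0.68, loss 32%.

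The loss is smaller because variation between providers dominates this comparison whether or not the score is split.

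**3. Mean of the three post values, clustered.** The 0.8 correlation becomes 0.590 at 50/50 and 0.556 at 80/20 after the split. The variance is proportional to (1 + 2r)/3 + 7 × ICC, taking the provider effect as stable over time. For the score it is 0.867 + 1.4 = 2.267.
- 50/50: binary 0.727 + 0.897 = 1.624; efficiency 0.637 × 2.267 / 1.624 = 0.89, loss 11%.
- 80/20: binary 0.704 + 0.736 = 1.440; efficiency 0.490 × 2.267 / 1.440 = 0.77, loss 23%.

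Without clustering the same contrast loses 24% to 40%.

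**4. Within-child change from baseline.** A stable provider effect cancels. The efficiency is E × (1 − 0.8) / (1 − binary correlation).
- 50/50: 0.637 × 0.2 / 0.410 = 0.31, loss 69%.
- 70/30: binary correlation 0.577; 0.576 × 0.2 / 0.423 = 0.27, loss 73%.
- 80/20: 0.490 × 0.2 / 0.444 = 0.22, loss 78%.

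The number of post values cancels from this ratio, so the result is the same for one or three. The loss is large because a score that tracks well within a child becomes a much noisier two-level variable.

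**The case against.** The strongest reply is that the plan may not commit to this analysis at all. The split appears once, in parentheses, in an instrument description. The outcome lists in Sections 3 and 9.1 omit it, and Section 9.4.2 never assigns MARS-A to a model. That stands as far as it goes. The use of a generalized linear mixed model follows only if the two-level form is the one analysed. Even so, the synopsis is the only place that says how MARS-A will be scored, and it says two levels.

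A reader might infer that the plan discards 36–51% of the information, or that 64 dyads act like about 41, 37 or 31 (64 × 0.637, 0.576, 0.490). The documents do not support either as fact. Both rest on normality, an unstated split and independent children, and this trial randomises providers. With a design effect of 2.4, 64 dyads are worth about 27 independent children (64/2.4) even with the score kept whole. Nor is 64 the only supportable number: 85 recruited dyads at 20% attrition give 68, and the 90% completion in Section 9.4.1 gives 72 (of 80) to about 76 (of 85).

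It is also tempting to call the binary model fragile with eight providers. Eight clusters limit between-arm inference in the linear model as well, and no calculation here shows how much worse the binary model would be.

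Finally, MARS-A is one of many secondary measures in a feasibility trial, with no power claim of its own. That is correct, and it limits the weight of the point.

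**Conclusion.** The point holds as a small improvement to a secondary endpoint. The synopsis dichotomises MARS-A with no cut-point or reason, although the plan's stated support for the measure concerns scores and its script includes partial gains. Precision is lost in every scenario computed, but the documents fix no single figure. For a normal score and splits from 50/50 to 80/20:

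| Comparison | Loss |
|---|---|
| One comparison, independent children | 36–51% |
| One comparison, ICC 0.2, 8 dyads per provider | 19–32% |
| Mean of three post values, same clustering, correlation 0.8 | 11–23% |
| Within-child change, correlation 0.8 | 69–78% |

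The last row is closest to an arm-by-post contrast, but it leans most on the 0.8 correlation holding for MARS-A and on a provider effect that does not vary over time. A more extreme split, or a skewed or ceiling-bound score, would change every row.

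**What to change.** State in Section 9.4.2 that the MARS-A score will be analysed as a continuous outcome in a linear mixed model with provider and patient random effects, and that the test is the arm-by-post (or arm-by-time) contrast. The contrast must be written out, because the ACQ model cannot simply be copied: as written it tests β3, the coefficient of a pre/post indicator, and has no arm-by-time term.

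Check the score's distribution as Section 9.4.1 already plans. Prespecify the cut-point for high adherence before unblinded data are seen, and report percent high by arm and month as a supportive summary. Bring the synopsis entry into line.

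The cost is one line in the analysis plan and no new data. The one drawback is that a mean score difference is slightly harder to read than a percentage, which the supportive summary covers.
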